Recent studies have suggested that genetic variation could be a reasonable explanation to the considerable differences on vitamin D levels among population independently of latitude and sunlight exposure. (Valdivielso 2004) Heritability of vitamin D levels has been reported to range from 28.8% to 68.9% in an adolescent twin study and up to 80% in a genome-wide linkage scan. (Uinterlinden 2004, Santos 2012). Identifying genetic variants in the form of single nucleotide polymorphisms (SNPs) has been one of the key methods for identifying genetic variants associated with vitamin D levels. The data would be helpful for identifying those who may be at risk of deficiency and targeting treatment to reduce the impact of vitamin D deficiency. The study will undertake a Genome-wide analysis of leukocyte gene expression and its correlation with differences in vitamin D status. The Vitamin D Receptor (VDR) is a nuclear transcription factor which controls expression of a wide range of genes, including several that encode cytochrome P450 enzymes and cytokines. Human leukocytes are known to express the VDRencoding gene and it is therefore envisaged that differences in vitamin D responses of individuals could be reflected by differences in leukocyte gene expression. Therefore we propose to analyse genomewide transcriptomic expression within leukocytes of selected participants in order to associate specific signal transduction and metabolic pathways to respective vitamin D responses. Circulating 25(OH)D concentrations have been shown to be strongly related to SNPs located on exons of the vitamin D binding protein gene: i.e. minor SNP variants of DBP-1 (rs7041, GG®TT (17.5%) and DBP-2 (rs4588, CC®AA (9%), resulting in 10-13% lower circulating 25OHD levels.

Our results will firstly enable determination of how important (as a % contribution) diet, sunlight exposure and genetic factors are to vitamin D status when directly comparing, using the same methodology, same ethnicity populations living in a Southern Hemisphere (where there is abundant sunlight exposure) and in a Northern Hemisphere (where there is only sufficient sunlight exposure during the months April to September).

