3.0 Experimental Design

Two controlled, randomized, double-blind clinical trials will be developed and undertaken (one in Brazil and the other in the UK) with an intervention period of 12 weeks.

A questionnaire to screen for the relevant inclusion and exclusion criteria (see section A) will be administered in order to select 80 Brazilian female subjects, aged 20 to 59 years, in each of the two countries. The women selected will be randomly divided into two groups: Placebo Group and Supplemented Group, the latter will receive 600UI UI of vitamin D.

The first clinical trial will run in the UK from October 2016 to March 2017 (autumn-winter) and then the second will run in Brazil from April 2017 to September 2017 (autumn-winter). After the analysis of the effect of vitamin D supplementation compared to placebo, the results obtained in the supplemented group will also be analysed according to the genotypes for SNPs in the VDR gene.

We have chosen 12 weeks (3 months) as the supplementation period as we consider this to be ample time for 25OHD levels to rise (half-life of 25OHD is 3 weeks) and this has been demonstrated to be an effective timeframe for supplementation of vitamin D in previous studies.

We have chosen 600IU to enable the study to be relevant to the new IOM US recommendations for vitamin D, which are currently the reference document used in Brazil, even though the Brazilian nutritional table remains with the daily intake recommendation of 200 IU, which was the IOM recommendation in 1997. Compliance will be checked by compliance interviews during the trial and by empty packaging count.

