We will genotype vitamin D related genes in DNA isolated from the study blood samples, DNA will be extracted and vitamin D polymorphisms will be determined by our genetic labs. These will include known candidate variants (VDR, vitamin D binding protein, CYP2R1, CYP27A1, CYP27B1, and CYP24A1), as well as variants identified by the ongoing genome-wide association analyses on 25OHD. We will construct a genetic risk score based on these polymorphisms. The Genome-wide expression profiling of RNA from leukocytes will focus on 48 participants (each at two sampling time points) that represent equally both groups, encompassing the best and worst supplementation-responders in each group. We will identify the complete spectrum of genes that are, by statistical criteria, either significantly up-or down-regulated (i.e. differentially expressed) between groups. The major comparison will be between the 'good' and 'poor' responders in each group; gene expression prior to supplementation will be compared to after supplementation for each subject analysed.

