7.0 Study Evaluation and Statistical Analysis

Statistical analysis will be undertaken with support from the University of Surrey statistical department. Data will be checked for normality using appropriate testing. Appropriate parametric/non-parametric analysis will be applied.

The database will be stored and analysed using SPSS ® version 13.0.

The descriptive analysis, including mean ± standard deviation, median and lower limit and higher will be held for all quantitative variables Data will be checked for normality using appropriate testing. Appropriate parametric/non-parametric analysis will be applied. Student t test or Mann-Whitney test, depending on the distribution of data, will be applied to evaluate differences between supplemented and placebo. For analysis between Brazil and UK groups an ANOVA test will be undertaken. Linear correlation, Pearson or Spearman, will be calculated in accordance with the presence / absence of normal distribution, respectively, between vitamin D intake, sun exposure, skin pigmentation and vitamin D serum concentration. Multiple linear regression analysis will be performed to determine the variants that influence blood concentrations of vitamin D. In order to determine whether supplemental response differs between genotypes, these will be separated into wild homozygotes, heterozygotes and homozygotes for the variant. In this approach, the results will be evaluated with the test ANOVA or Kruskal-Wallis, in cases of variables with normal distribution or not, respectively. To describe the relationship between food intake aspects and features biochemical independent of energy intake, intake values of nutrients of interest will be adjusted to energy in accordance with the method. Significance considered as standard will be 5%.

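### The genotype test of response to supplementation names no baseline adjustment, so it loses precision and can mix a genotype effect on response with a lower starting 25OHD

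*Combined protocol and SAP*

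**What the plan says.** Section 7.0 assigns the genetic response question to a three-class comparison: "these will be separated into wild homozygotes, heterozygotes and homozygotes for the variant", after which "the results will be evaluated with the test ANOVA or Kruskal-Wallis", depending on normality. It names no covariate, country term or genetic model, and it does not define response as a change or a final level. The significance level is 5%.

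Section 3.0 places the analysis in one arm: "the results obtained in the supplemented group will also be analysed according to the genotypes for SNPs in the VDR gene". The same section lists six candidate genes and adds "We will construct a genetic risk score based on these polymorphisms", but section 7.0 does not say how that score is analysed.

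Three other statements bear on the test:
- H2 (section 2.3) makes response depend on baseline 25OHD.
- H5 (section 2.3) expects strong genetic influences on the change in 25OHD, similar in both groups. I read the groups as the two countries.
- Section 1.0 describes "minor SNP variants of DBP-1 (rs7041, GG®TT (17.5%) and DBP-2 (rs4588, CC®AA (9%), resulting in 10-13% lower circulating 25OHD levels".

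Section 7.0 also plans a multiple linear regression for blood concentrations of vitamin D, without giving covariates or genotype coding.

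**The concern.** If response depends on baseline (H2) and some genotypes start lower (section 1.0), genotype is linked to response through baseline alone. Women with the lowering variant could appear to respond better simply because they began lower. H5 and secondary objective (viii) concern genetic influence on the response, and an unadjusted comparison cannot separate the two routes.

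Baseline 25OHD is also a measured predictor of the outcome. Leaving it out keeps variance in the error term that could be removed, in an analysis that has few women. The supplement-versus-placebo comparison is not affected.

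**Working it through.** The protocol states no power or sample-size figure for the genotype test, so there is none to reproduce.

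**Numbers analysed.** Section 3.1 gives 40 supplemented women per country including 20% drop-out: 40 x 0.8 = 32 completers, or 64 over both countries.

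**Smallest class.** Assume that the 17.5% and 9% in section 1.0 are minor-homozygote frequencies.
- One country: 32 x 0.175 = 5.6 and 32 x 0.09 = 2.9.
- Both countries: 64 x 0.175 = 11.2 and 64 x 0.09 = 5.8.
- At 9%, the binomial chance of two or fewer among 32 is 44%.

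These are binding-protein SNPs. No frequency is given for any VDR SNP.

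**Effect of ignoring baseline.** The documents give no SD for 25OHD or its change, so the following are assumptions: SD of change 1, SD of baseline 1, slope of change on baseline -0.5. Baseline then explains 0.25 of the variance of change, and adjustment multiplies the noncentrality by 1/(1 - 0.25) = 1.33.

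For an additive effect b per allele, the noncentrality is N x 2q(1-q) x b^2. Under Hardy-Weinberg, q = sqrt(0.175) = 0.418 or sqrt(0.09) = 0.30, so 2q(1-q) = 0.487 or 0.420. With b = 0.4, N = 64 and q = 0.418, it is 64 x 0.487 x 0.16 = 4.98 unadjusted and 4.98/0.75 = 6.64 adjusted. Power at two-sided 5% (noncentral F):

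| N, homozygote frequency | Three-class, unadjusted | Three-class, adjusted | Allele count, unadjusted | Allele count, adjusted |
|---|---|---|---|---|
| 32, 17.5% | 25% | 32% | 33% | 42% |
| 32, 9% | 22% | 28% | 29% | 37% |
| 64, 17.5% | 48% | 61% | 59% | 72% |
| 64, 9% | 42% | 54% | 53% | 65% |

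Simulation with recessive and dominant effects of 0.8 SD also favours adjustment. Over all three genetic models the three-class test gains about 4 to 13 points from the baseline term.

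**Mixing with baseline.** Suppose genotype has no effect on response but lowers baseline by 0.3 SD per allele. The unadjusted change then shows (-0.5) x (-0.3) = +0.15 SD per allele. The noncentrality at N = 64, q = 0.418 is 64 x 0.487 x 0.15^2 = 0.70.
- The unadjusted three-class test rejects about 7% of the time with 32 women and 10% with 64, at either frequency.
- The unadjusted allele-count test rejects about 8 to 9% and 12 to 13%. Changing the coding alone would make the mixing worse.
- With baseline in the model, simulated rejection is about 5%.
- With a shift of only 0.15 SD, the unadjusted three-class rate is about 5 to 6%.

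**Allele count against three classes.** In the table the allele-count test is ahead by about 7 to 12 points, but the table assumes additivity. Making the same 0.8 SD homozygote contrast recessive reverses the order (simulated, unadjusted, three-class then allele count):
- 64 women: 54% against 43-44% (17.5%), and 33% against 23% (9%).
- 32 women: 28% against 23% (17.5%), and about 17-18% against 13.5% (9%).

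With baseline in the model the loss reaches about 13 points (64 women, 17.5%: 66% against 53%). A dominant 0.8 SD effect is roughly neutral: with 64 women, 75% against 71% (17.5%) and 80% against 81% (9%).

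**Remaining limit.** Without baseline adjustment, the additive effect detectable at 80% power with 32 women is 0.83 SD (three-class) or 0.73 SD (allele count) per allele at 17.5%, and 0.89 or 0.79 SD at 9%. With 64 women it is 0.57 or 0.51 SD, and 0.61 or 0.55 SD.

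**The case against.** **A regression is already planned.** It is, but section 7.0 directs it at blood concentrations, leaves covariates and coding open, and gives the response question to the three-class test. It does not supply the adjustment.

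**Adjustment changes the question.** This stands. Genotype is not randomised and may act through baseline. The adjusted coefficient is the effect beyond baseline level, whereas H5 speaks of the change. Both should be shown.

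**The sizes are assumed.** This also stands. The protocol's only genetic effect size, "resulting in 10-13% lower circulating 25OHD levels", concerns circulating level, not response. If half of it falls on each allele and the SD is 30-50% of the mean (not in the documents), the effect is about 0.1 to 0.2 SD per allele. At that size the allele-count gain is only about 0 to 2 points with 32 women and 1 to 4 with 64.

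**Stronger readings that a reader might infer.**
- That an allele-count test should replace the three classes at no cost. The documents nowhere say the effect is additive, and section 1.0 gives only homozygote contrasts. The recessive results show a real loss, and the three-class test has 54% power in one such case, so a recessive effect is not out of reach anyway.
- That the planned VDR test has nearly empty cells. The frequencies are for another gene, and the plan does not say whether the countries are analysed separately.
- That the risk score and wider gene list are defects of the same kind. They are mainly missing detail, and testing more genes at 5% would add multiplicity.

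**Conclusion.** The concern holds on baseline adjustment. The protocol's own premises (H2 and section 1.0) imply that an unadjusted genotype comparison loses precision and can confuse response with starting level. Under the assumed slope of -0.5, the loss for the three-class test is about 4 to 13 points of power. The false-positive rate is 7 to 10% if the variant shifts baseline by 0.3 SD per allele, and close to nominal if the shift is half that.

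The choice between allele count and three classes is a trade-off to settle in advance, not an error in the plan. The cell counts of about 6 and 3 of 32 per country, or 11 and 6 pooled, rest on reading the section 1.0 percentages as homozygote frequencies. They apply to the binding-protein SNPs only.

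This is a worthwhile correction to a secondary objective. Power stays low for moderate effects whichever version leads.

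**What to change.** Amend section 7.0 as follows.

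1. Analyse week-12 25OHD in the supplemented women by linear regression on genotype, adjusted for baseline 25OHD and country.
2. Add a genotype-by-country term to address H5's claim of similarity, which a country main effect cannot test. Report it with a confidence interval. With equal halves, a between-country difference in genotype slopes has about twice the standard error of the pooled slope, so a non-significant result would not show similarity.
3. Report the allele-count (1 df) and three-class (2 df) versions, and name the leading one before unblinding.
4. Show the unadjusted change by genotype beside the adjusted estimate, and state that the latter is the effect beyond baseline level.
5. Use all consenting supplemented women. Section 4.1 places genotyping under the selection of 48 best and worst responders; ordinary regression in a sample chosen on the outcome would be biased.
6. Label the analysis exploratory.

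The cost is analysis wording, one baseline degree of freedom and the country terms. Baseline and final 25OHD are already collected. If section 4.1 means that only the 48 are genotyped, step 5 also requires genotyping the remaining consenting supplemented women from blood already planned for genetic profiling.

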2.3 Hypothesis

The study hypothesis that, during winter, vitamin D supplementation is required to obtain Vitamin D optimal levels in Brazilian women residing in the UK as well as Brazilian women residing in Brazil and that this response is dependent on the initial levels, being also influenced by sunlight exposure, skin pigmentation and polymorphisms of the vitamin D receptor gene.

H1: Dietary intakes of vitamin D are too low and sunlight exposure is insufficient for optimal vitamin D status in Brazilians living in the UK and Brazilians living in Brazil.

H2: The response of subjects to vitamin D supplementation is dependent on baseline 25OHD levels.

H3: Response to supplementation is influenced by sun light exposure.

H4: Skin pigmentation is an influential factor on vitamin D optimal levels.

H5: There will be strong genetic influences on 25OHD changes in response to vitamin D supplementation; these will be similar in both groups.

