3.3 Selection & Withdrawal of Participants

3.3.1 Inclusion Criteria

- Brazilian nationality
- Female
- Aged 20-59 years

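### The genotype-response test is unadjusted in women selected only by nationality, so differences related to ancestry or skin pigmentation could appear as, or hide, a SNP effect.

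*Combined protocol and SAP*

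**What the plan says.** - **Genotype test.** Section 7.0, on whether response to supplementation differs by genotype: "these will be separated into wild homozygotes, heterozygotes and homozygotes for the variant", and then "the results will be evaluated with the test ANOVA or Kruskal-Wallis", the choice depending on normality. No covariate is named.
- **Who is analysed.** Section 3.0 places the VDR genotype analysis in the supplemented group. It does not say whether the two countries are pooled.
- **Who can enter.** Section 3.3.1 lists "Brazilian nationality", female sex and age 20 to 59. Section 1.0 speaks of "same ethnicity populations living in a Southern Hemisphere" and in the Northern Hemisphere, but the available text gives no criterion or measurement of ethnicity or ancestry.
- **What the protocol expects.** Section 2.3 describes response as depending on initial levels and "being also influenced by sunlight exposure, skin pigmentation and polymorphisms of the vitamin D receptor gene". H4 adds: "Skin pigmentation is an influential factor on vitamin D optimal levels".
- **Where pigmentation is used.** Section 7.0 names it once, in pairwise correlations "between vitamin D intake, sun exposure, skin pigmentation and vitamin D serum concentration".
- **The planned regression.** "Multiple linear regression analysis will be performed to determine the variants that influence blood concentrations of vitamin D". No covariates are listed.

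**The concern.** Randomisation protects the comparison of vitamin D with placebo. It does not protect a comparison of genotype classes within the supplemented arm. There, a SNP with no effect on vitamin D metabolism can look associated with response if two things hold together: its allele frequency varies with ancestry, and response varies with ancestry, for instance through pigmentation.

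The protocol hypothesises a link between pigmentation and response. Entry by nationality does nothing to exclude a link between ancestry and allele frequency. The planned test has no term that could separate the two.

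At stake is H5, which predicts strong genetic influences, and secondary objective (viii), which compares high and low responders. A SNP could be credited with a pigmentation effect, or a real SNP effect could be cancelled by one running the other way.

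**Working it through.** **Plan's own figure.** There is none for the genotype analysis. Section 3.1 sizes only vitamin D against placebo, and is used here just for the number of women.

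**Number of women.** Supplemented women per country: 40. After the 20% drop-out in Section 3.1: 40 × 0.80 = 32. Both countries pooled: 2 × 32 = 64.

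**Assumptions, none from the documents.** Two ancestry strata of equal size; mean allele frequency 0.35; allele-frequency gap *g* between strata of 0.1 to 0.3; mean response differing by *d* = 0.5 to 1.0 within-stratum SD; no true genotype effect.

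**Step 1: spurious slope per allele.** Let G be the allele count and Y the response.

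- cov(G, Y) = 2 × *g* × *d* × 0.25
- var(G) = mean of 2p(1−p) over the strata + *g*²
- *g* = 0.1 (frequencies 0.30 and 0.40): var(G) = (0.42 + 0.48)/2 + 0.01 = 0.46. With *d* = 0.5, slope = 0.025/0.46 = 0.054 SD.
- *g* = 0.3 (frequencies 0.20 and 0.50): var(G) = (0.32 + 0.50)/2 + 0.09 = 0.50. With *d* = 0.5, slope = 0.075/0.50 = 0.15 SD. With *d* = 1.0, slope = 0.15/0.50 = 0.30 SD.

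A SNP that does nothing would thus show about 0.05 to 0.30 SD per allele.

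**Step 2: false-positive rate of the planned test.** The plan compares three genotype classes, so a three-group F-test was simulated at nominal 5%.

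| Difference in response between strata | 32 women (one country) | 64 women (pooled) |
|---|---|---|
| 0.25 SD | near 5% | up to about 6% |
| 0.5 to 1.0 SD, gap 0.1 to 0.3 | about 5% to 13% | about 6% to 26% |

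With 32 women and a 0.5 SD difference alone, the range is about 5% to 7%. The top of each range needs both the largest gap and the largest difference. A repeat run put the 64-woman maximum at 25%, so the upper figures carry about a percentage point of simulation error.

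**Step 3: check on the mechanism.** A second simulation used mean allele frequency 0.4. With no allele-frequency gap, or no difference in response, the unadjusted rate stayed near 5% (4.5% to 5.5% over all sample sizes tried). With a gap of 0.2 and a difference of 1.0 SD it was 8.7% with 32 women and 12.0% with 64. Widening the gap to 0.4 raised these to 19.1% and 37.9%, which shows how far the size depends on inputs the documents do not supply.

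**Step 4: does adjustment work?** With the true stratum in the model, the rate returned to 4.5% to 5.1% under the main assumptions and 4.0% to 5.6% in the second simulation. With only a proxy correlated 0.5 with the stratum (also an assumption), the worst case with 64 women fell from about 26% to about 17%. An imperfect proxy removes part of the bias, not all of it.

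**The case against.** **An adjusted analysis is already planned.** Section 7.0 includes a multiple linear regression, and pigmentation is named in the sentence before it. It would be wrong to infer that the plan has no multivariable model. But its outcome is concentration rather than response, its covariates are not given, and the genotype question has its own named test. The regression could be extended to do this job; as written it does not.

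**The size is speculative.** This stands. The documents give no strata, no allele-frequency gap and no response difference by ancestry. A difference of 1.0 SD exceeds the 0.6 SD treatment effect for which Section 3.1 sizes the trial. With one country and moderate inputs the inflation is slight.

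**Level is not response.** H4 concerns levels, and a stable difference in level cancels in a change score except through dependence on baseline, which H2 expects. Section 1.0 also says that UV of the right wavelength is absent in the UK from end October to end March, which covers most of that trial. Pigmentation's direct route to response is therefore weaker there. This argues for including baseline 25OHD and for modest expectations in the UK. It does not answer the point for Brazil, and Section 2.3 still names pigmentation as an influence on response in both countries.

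**A false-positive rate of one in three.** A reader who models a per-allele trend test under the main assumptions would get up to 33% with 64 women and 19% with 32. The plan does not use that test. For its three-group comparison the corresponding upper figures are about 26% and 13%.

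**Scope.** The genetic question is a secondary objective, and the randomised comparison is unaffected. Both are true.

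**Conclusion.** The concern holds as a gap in the specified method. The genotype-response test is unadjusted, genotype is not randomised, ancestry is neither restricted nor, in the available text, recorded, and the protocol itself treats pigmentation as a determinant of response. Nothing else in Section 7.0 closes the gap.

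Whether bias will occur, and how large it would be, cannot be settled from the documents. The ranges of about 5% to 13% (one country) and 6% to 26% (pooled) are illustrative and rest wholly on the assumptions above. A reader might infer that any genotype finding from this trial would be spurious; the documents do not support that, because the bias needs both allele frequency and response to vary with ancestry. The case for change is that protection is cheap and that H5 is a named hypothesis.

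**What to change.** Make the main genotype analysis a linear regression of change in 25OHD on genotype class, with baseline 25OHD, skin pigmentation, and country if the countries are pooled; add self-reported colour or ancestry if it is recorded. State whether the countries are pooled. For each SNP, report the estimate and confidence interval with and without adjustment, and base the H5 conclusion on the adjusted estimate. Avoid a rule that discards effects which lose significance on adjustment: in samples this small, chance alone would often trigger it.

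State in the plan that pigmentation is an imperfect proxy for ancestry and that residual stratification remains.

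**Cost.** Plan wording and two or three degrees of freedom (more if colour or ancestry enters as several categories). With 32 women, residual degrees of freedom fall from 32 − 3 = 29 to 27 with two covariates; with 64, from 61 to 58 with three. One practical check is needed: the visit activities in Section 4.1 do not list a pigmentation measurement. It may sit in a questionnaire that is not reproduced, so the sponsor should confirm how and when it is recorded. With baseline in the model, the estimate is the difference in change between genotypes at the same starting 25OHD, and the plan should say so.
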